The recruitment and screening period for potential participants will be 12 months (in order to identify 70 eligible participants) following the decision to initiate the protocol. It is expected that 70 participants will be informed and consented, and enrolled in the study, by approximately 12 months. Treatment for each participant will be carried out for a total of 9 months, or less if there is evidence of clinical

CONFIDENTIAL

and mycological cure prior to that time. The 9-month follow up visit will serve as the primary efficacy endpoint, in keeping with the usual expected minimum 7 to 9 -month duration of time expected for a full replacement of the visible nail plate in a typical adult human. Thereafter, a 3-month period will be allotted for completion of mycological testing and data collection. An additional 3 months will be allotted for completion of the analyses and 3 more months to write the report describing the study and submission of the manuscript for consideration for publication in a refereed journal. It is, therefore, estimated that the duration of time necessary for the completion of this protocol, data analysis, and preparation of the final report, will be approximately 35 months.

Study Centers

This study will be carried out at multiple clinical offices, under the guidance of different CITI-trained investigators, including:

- [name], DPM; Ankle & Foot Associates, [contact] (cell) Contact: Self; [contact], [name]. Site A
- [name], DPM; St Cloud Foot & Ankle; [contact] (cell) Contact: self; [contact] [name]. Site B
- [name], DPM; National Foot and Ankle, [contact] (cell) Contact: Self; [contact], [name]. Site C
- 4. [name], DPM; Family Foot Care, [contact] (cell) Contact: Self; [contact], [name]. Site D
- [name], DPM (the Principal Investigator); Foot & Ankle Specialists of Nevada, [contact] (cell) Contact: Self; [contact], [name]. Site E
- [name], DPM; A Step Ahead Foot and Ankle, [contact] (cell) Contact: Self; [contact], [name]. Site F
- [name], DPM, [name], DPM; The Division of Podiatry at The GW Medical Faculty Associates, [contact]) Contact: Office; [name]. Site G.

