It should be noted that the method of supply and application of both the placebo and the active topical nail solution is consistent with the standard method of use approved by the FDA monograph for use of an over-the-counter topical cosmetic agent, in accordance with the existing FDA monograph approved method for the treatment of dystrophic nails (see Tolcylen[™] label, Attachment 1). Participants in each group will be verbally instructed in the proper method of application of the topical solution and will also receive written instructions describing the study regimen and application technique (Attachment 2).

Upon arrival to the clinic for follow-up evaluation and care, the study participant will meet with a blinded investigator in the treatment room. The blinded investigator will review the study protocol and discuss any questions that the participant may have. The blinded investigator will inspect the participant's affected toes and procure the required information (clinical and photographic data) as delineated in this protocol.

Duration of Administration

For participants in both groups, maintenance of topical application of the assigned solution on the mycotic toenail/s will continue for a period of up to 9 (nine) months, for the purposes of the study. This duration of application is based

CONFIDENTIAL

on an average adult nail growth rate of 9 months for emergence from the proximal nail fold to the distal margin of the nail bed. Follow-up inspections will take place at 3, 7, and 9 months, following randomization and initiation of the treatment process. If participant shows clinical and mycological clearance prior to 9 months follow up, the participant may discontinue application of the topical nail solution if desired, in keeping with general clinical practice. The primary efficacy endpoint will occur at the minimum duration of 7-9 months, in keeping with the aforementioned and subsequently reviewed, proposed study timeline.

Timeline

The general design of this study is that of a randomized, controlled trial, wherein the intervention arms of the study consist of the application of either placebo or active topical nail solution, to be performed on volunteer human participants. The proposed study timeline is denoted in Table 2 and Fig. 1, below.

Milestone	Months
Screening visit and enrollment	12
3-month follow up visit	15
7-month follow up visit	18
9-mont follow up visit	21
Data analysis	27
Submit for publication	30

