A visible nail plate involvement score (Table 3, below) will be used to assess the clinical appearance of an involved toenail, at baseline and then repeated at each follow up visit. This score was designed to provide a continuous numeric value to rate the gross clinical appearance of dystrophic and/or mycotic toenails. The score ranges from a low of 7 to a maximum of 27, with a lower score indicative of a more normal appearing toenail and a higher score indicative of more advanced toenail dystrophy based on gross clinical inspection. This scoring scale was deemed reliable when tested for inter- and intra-rater reliability; wherein, 4 observers rated 40 nails on two separate occasions 3 weeks apart (Pearson's product-moment correlation coefficients for inter-rater reliability ranged from

CONFIDENTIAL

0.8849 to 0.9609 and the intra-rater reliability ranged from 0.8768 to 0.9687). Pearson's product-moment correlation coefficients range from -1 (100% negative association, or perfect inversion) to +1 (100% positive association, or perfect agreement), with a value of zero indicative of the absence of an association. In general, correlation coefficients with absolute values ranging from 0.60 to 1.00 are considered strong, and those <0.40 are considered weak. Our assessment of this scoring scale for visible toenail involvement indicated strong positive agreements for between and within rater correlations. The index toenail will be rated either by the blind site investigator, or submitted as a photograph for blind study coinvestigators to score. A decrease in the VNPIS of \geq 60% at any follow up visit will be considered a clinical cure.

	/	
Nail plate characteristics		Point/s
Type of apparent onychomycosis [select one]	White superficial	1
	Distal subungual	2
	Proximal subungual	3
	Any combination of above	4
Longitudinal segmental involvement of visible nail	≤ Distal half	2
plate (location of gross visible nail plate	> Distal half, excluding lunula	3
involvement) [select one]	Extending proximal to lunula	4
Apparent percentage involvement of visible nail	≤ 25%	2
plate [select one]	> 25% ≤ 50%	3
	> 50% ≤ 75%	4
	> 75%	5
Overt gross appearance of involved nail. For	Overtly thickened nail plate	2
thickness, inspect distal margin of visible nail plate	Lytic, overtly lifted from nail bed	3
and bed (including hyperkeratosis of nail bed	Onychauxis, gryphosis,	1
attached to plantar surface of nail plate) compared	clubbed, ram's horn shape	4

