In the event that a participant withdraws from the study prior to the termination of the designated follow-up period, every attempt will be made to inquire as to the rationale that the participant used in deciding to withdraw. Moreover, permission will be sought to collect at least survival (time to event) data. In light of the importance of complete follow-up, in relation to the integrity of the research study, the following steps will be taken prior to concluding that a participant is definitely lost to follow-up:

- 1. Three separate telephone calls on three separate days, each to the participant's home and place of work.
- 2. A letter sent to the participant's residence via certified mail, asking the individual to contact the study center to discuss their progress and participation in the study.
- 3. A telephone call to the participant's next of kin, to inquire as to the participant's whereabouts and participation in the study.

Statistical Plan

Power and Sample Size Determination

CONFIDENTIAL

Analyzing for the dichotomous outcome, either cured or not cured, using Fisher's exact test for independent groups (active topical nail solution and placebo), in a prospective randomized fashion, expressing the alternative hypothesis as two proportions, at $\alpha = 0.05$, and $\beta = 0.08$, with the event rate in controls as 0.01 and the that in cases as 0.3, and using a 1:1 ratio of cases to controls, we will need 29 participants in each treatment group, or 58 participants overall, to be able to detect a statistically significant difference between the treatment arms. In anticipation of dropouts, limited site enrollment and center effects and multiple center effects (6 clinical sites), an additional 20% will be added in an effort to ensure statistical power. Therefore, a total of 70 participants will be enrolled and randomized, subject to the data safety monitor's surveillance and recommendation.

Statistical Methods

The primary endpoint in this study is the mycological presence or absence of fungal hyphae in fragments of the index toenail as viewed on the microscopic PAS stain, following the application of active topical nail solution, or placebo nail solution, to participant's mycotic toenails.

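### Clinical cure is met by a 60% fall in VNPIS at any one follow-up visit and need not still be present at month 9

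*Protocol*

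**What the plan says.** The section on the Visible Nail Plate Involvement Score has the nail scored "at baseline and then repeated at each follow up visit". It then states that a fall of 60% or more "at any follow up visit will be considered a clinical cure". Duration of Administration gives the schedule: "Follow-up inspections will take place at 3, 7, and 9 months". There are therefore three occasions on which the threshold can be met. No section asks for the fall to be confirmed, to persist or to be present at the last visit, and none says what happens to the classification if it is lost.

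On timing, Study Duration says "The 9-month follow up visit will serve as the primary efficacy endpoint", while Duration of Administration says "The primary efficacy endpoint will occur at the minimum duration of 7-9 months". The Research Question expects a higher incidence of improvement on active treatment, on both clinical and mycological grounds.

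The rule does not reach the main analysis. Statistical Methods says "The primary endpoint in this study is the mycological presence or absence of fungal hyphae in fragments of the index toenail", as seen on PAS stain, and lists VNPIS as a secondary endpoint in the form of a change in score. Missing later visits are filled by last observation carried forward (When and How to Withdraw Participants; Participant Population(s) for Analysis).

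**The concern.** The clinical half of the hypothesis is about incidence, and the VNPIS section holds the only numerical definition of clinical cure in the protocol. Taken at its word, one crossing of the threshold is enough. Two things follow. A nail that improved and then deteriorated is counted with nails that are clear at the end of treatment. The rate also depends on attendance, since a completer has three chances and someone who leaves after month 3 has one.

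The protocol justifies its duration by an "average adult nail growth rate of 9 months for emergence from the proximal nail fold" to the distal margin. On that figure about 3/9, or one third, of the plate has been replaced at month 3, so a month-3 crossing does not describe a fully regrown nail. At stake is a reported clinical cure rate that may exceed the proportion clinically cured at month 9, by an amount the reader cannot see.

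**Working it through.** **1. The plan's own figures.** Table 3 gives a minimum of 1 + 2 + 2 + 2 = 7 and a maximum of 4 + 4 + 5 + (2 + 3 + 4 + 5) = 27, which reproduces the stated range of 7 to 27. The sample size also reproduces. With event rates of 0.01 and 0.30, 29 per arm and a two-sided Fisher's exact test at 0.05, exact power is 0.843; 58 × 1.2 = 69.6, rounded to 70. VNPIS does not enter that calculation.

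**2. The rule applied to one case.** Baseline 20, month 3 score 8: (20 − 8)/20 = 60%, a clinical cure. Month 9 score 20: (20 − 20)/20 = 0%. Under the any-visit wording this participant remains a clinical cure.

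**3. The two definitions side by side** (Y = threshold met, N = not met, – = participant has left):

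| Months 3 / 7 / 9 | Any visit | Month 9, with last observation carried forward |
|---|---|---|
| Y / Y / Y | cured | cured |
| N / N / Y | cured | cured |
| Y / N / N | cured | not cured |
| N / Y / N | cured | not cured |
| Y / Y / N | cured | not cured |
| Y / – / – | cured | cured (carried forward) |
| N / – / – | not cured | not cured |

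With month 9 observed, any-visit rate − month-9 rate = proportion meeting the threshold at month 3 or 7 but not at month 9. This is never negative. Carrying forward does not remove it, because there is nothing to fill when month 9 is observed. Nor does a month-9 rule remove the sixth row.

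**4. Size.** The document gives no VNPIS cure rate and no rate of loss after early response, so the excess cannot be computed. With 70 participants at 1:1, or 35 per arm, each such participant moves that arm's rate by 1/35 = 2.9 percentage points.

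**5. Who can be affected.** With a floor of 7, a 60% fall requires 0.4 × baseline ≥ 7. Baseline 17 gives 6.8 (impossible) and baseline 18 gives 7.2 (possible). Only baselines of 18 or more can meet the rule, and the fall must be at least 0.6 × 18 = 10.8 points.

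**The case against.** The strongest reply is that no listed endpoint uses this rule. PAS is primary, VNPIS is analysed as a change in score, and the protocol names no between-arm test of the proportion clinically cured. That stands and limits the weight of the point. It does not remove it, because the hypothesis is framed as incidence and the protocol fixes this definition rather than leaving it open.

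A second reply is that the sentence may define status at each visit: cured at whichever visit the fall is seen. This is a fair reading, and the early-stopping provision ("If participant shows clinical and mycological clearance prior to 9 months follow up, the participant may discontinue application") could use such a status. But the protocol does not say so, and on that reading it still does not say which visit's status would be compared between arms.

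A third is that month 9 is not a settled anchor: one section says 7-9 months, and Diagnosis of Primary Outcome allows the repeat PAS at 3, 7 or 9 months. This is partly right. However, neither of the two statements that time the efficacy endpoint includes month 3.

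Three stronger inferences are tempting and are not supported:

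- **A large numerical inflation.** A reader might take a chance q of meeting the rule by fluctuation at each visit and compute 1 − (1 − q)³, so that 5% becomes 14.3% and 10% becomes 27.1% for independent visits. No value of q is in the document, and rating noise cannot supply one of that order. Take the lowest stated intra-rater correlation, 0.8768, an assumed score SD of 3 to 6, and normal error. The SD of a re-rating difference is SD × √(2 × (1 − 0.8768)), or 1.49 to 2.98 points. A 10.8-point fall is then 7.25 to 3.63 standard deviations, with chance about 2 × 10⁻¹³ to 1.4 × 10⁻⁴. This covers rating noise only, not trimming or real change.
- **That a month-3 fall is probably spurious.** VNPIS rates gross appearance, and early change in appearance is what it is meant to record. The growth figure shows that the plate is not replaced by then, not that the change is false.
- **That the active arm gains more.** Review of the Literature credits the product's delivery ingredients with a cosmetic effect, so this is possible. The document has no data on how early or how lasting that effect is.

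**Conclusion.** The point holds as a defect in the definition of a supporting outcome. As written, clinical cure can be earned at month 3 or 7 and kept after it has been lost, which does not fit an efficacy assessment at month 9 or at 7-9 months. The direction is certain: the any-visit rate is equal to or above the month-9 rate. The amount is unknown, and it is confined to participants with a baseline score of 18 or more on the stated range. The conclusion rests on the literal reading of one sentence and on the absence of any persistence requirement elsewhere in the protocol. A reader might infer that the trial's main result or sample size is compromised. It is not: the PAS comparison and the VNPIS change-score analysis do not use the rule.

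**What to change.** In the VNPIS section, state that clinical cure, when compared between arms, means a fall of at least 60% from baseline at the 9-month visit, for every randomised participant, including those who stopped applying the solution earlier. Report status at months 3 and 7 descriptively. Report by arm how many month-9 cures come from last observation carried forward, since an early cure in someone who then leaves would still be carried to month 9.

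The cost is a short change of wording. VNPIS is already scheduled at month 9, but that score must actually be obtained from participants who stopped application early. The clinical cure rate may be slightly lower.

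The wording that lets application stop early on clinical and mycological cure (Study Summary, Study Duration, Duration of Administration) does not refer to the VNPIS definition. The sponsor should reconcile those passages; this change concerns only the analysed outcome and leaves them as they are.

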Number of Participants	Analyzing for the dichotomous outcome, either cured or not cured, using Fisher's exact test for independent groups (active topical nails solution alone versus placebo nail solution), in a prospective randomized fashion, expressing the alternative hypothesis as two proportions, at $\alpha = 0.05$, and $\beta = 0.80$, with the event rate in controls estimated to be 0.01 and the event rate in cases estimated to be 0.3, and using a 1:1 ratio of cases to controls, 29 participants will be needed in each treatment group in order to identify a statistically significant difference, should one exist. In anticipation of dropouts, limited site enrollment, and center effects and multiple center effects (≥6 clinical sites), an additional 20% will be added in an effort to ensure statistical power. Therefore, a minimum of 70 participants will be enrolled and randomized, subject to the data safety monitor's surveillance and recommendation.
Diagnosis and Main Inclusion Criteria	The main clinical disease under evaluation is toe onychomycosis. Participants will be males and non-pregnant females 18 years of age or older that have been diagnosed with distal subungual onychomycosis (DSO) involving at least one toenail. Diagnosis of this condition is to be made on the basis of history, physical examination, and a mycological inspection that includes a tissue examination for fungal hyphae (PAS stain). Evidence of fungal hyphae will be considered a positive confirmation of the diagnosis of toenail onychomycosis.
Study Product and Regimen	All participants will be randomized to either the active topical nail solution group, antifungal solution treatment, or to the placebo nail solution group. The topical antifungal medication under investigation is Tolcylen [™] . It will be provided by Marlinz Pharma, Houston, TX, the study funding Sponsor. The topical therapy will be applied in accordance with the existing FDA-approved method for use of this cosmetic agent.
Duration of administration	Administration of the interventions, active and placebo, will continue for no longer than nine (9) months. Administration of the topical agent may stop sooner if clinical and mycological evidence of cures are identified prior to nine (9) months.

CONFIDENTIAL

ponson marine i narina	

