Reference therapy	Participants in the control group will apply a placebo topical solution to the involved toenail/s. Preparation of the placebo solution, dimethicone 5%, was undertaken with the aim of making it as close as possible to the active topical nail solution in terms of color and texture, and other physical characteristics. The placebo nail solution, like the active topical nail solution, meets the FDA's safe ingredient criteria for an over-the-counter topical agent. The placebo, like the active topical nail solution, will be supplied in three (3) 7.5 ml tubes with a controlled-release applicator mechanism that allows thin coat of the solution to be applied at a time, and the instructions for application specify that only thin coat of solution to be applied daily to under the leading edge, borders of the toenail and the entire surface of the toenail.
Statistical Methodology	All participants will be followed to the endpoint of the study, in accordance with the proposed timeline (see below). An intention to treat analysis will be used. Data analysis will entail descriptive statistical methods, including mean and standard deviation, or median and quartile, to describe demographic variables; as well as inferential statistical methods that will include two sample tests of the null hypothesis for differences between the two treatment groups both before and after active topical nail solution or placebo application, and for comparisons of pre-treatment and post-treatment results in single participants, for mycological tests and outcomes. The Wilcoxon rank sum (Mann Whitney) test for unpaired data will be used to identify differences between the two intervention groups both before and after active topical nail solution or placebo application, and the Wilcoxon signed rank test for paired data will be used for comparison of pre-treatment and post-treatment results in single participants, mycological tests, and the OnyCOE-t [™] and Visible Nail Plate Involvement Scores. Participants will be analyzed as randomized, and the last observation carried forward method will be used if a participant fails to complete the study protocol (lost to follow up for any cause, whether at-random or otherwise). The participants, as well as all observers and outcomes assessors, will be blind to

CONFIDENTIAL

Research Protocol

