- 5. Participant has an intact protective cutaneous sensation as measured with the lpswich test for loss of protective sensation (10-gram monofilament);
- 6. Participant has an intact cutaneous barrier, with or without the presence of hyperkeratotic lesions, with or without concomitant tinea pedis or

CONFIDENTIAL

interdigital maceration, or with or without a history of previous skin ulceration, but without active or current pedal ulceration;

- 7. Participant must be a satisfactory candidate for the proposed topical antifungal or placebo intervention;
- 8. Participant must display the ability to understand and give informed consent to participation, on a voluntary basis, in the research study.

Exclusion criteria for this study are:

- 1. Presence of dermatophytoma, defined as thick masses of fungal hyphae and necrotic keratin between the nail plate and nail bed;
- 2. Use of any systemic antifungal therapeutic agents within 7-months before the baseline visit, or topical antifungal agent on the feet within 1 month preceding the baseline measurement visit;
- 3. Candidate with moccasin tinea pedis involving greater than 50% of either plantar surface;
- 4. Candidate requires the use of narcotic analgesic or non-steroidal antiinflammatory drug/s for 48 hours prior to baseline visit or at any follow-up clinical evaluations;
- 5. Candidate has an active drug/alcohol dependence or abuse history;
- 6. Candidate has a loss of protective pedal sensation or open cutaneous compromise involving the ipsilateral foot;
- 7. Candidate has trauma to the nail that resulting in permanent nail plate discoloration or shape;
- 8. Candidate displays radiographic evidence of abnormal lytic or proliferative bone lesion in the toe/s of interest, including recent or healing of an acute fracture, if clinical inspection indicates the potential presence of subungual exostosis (radiographs will be obtained and paid for in the course of usual and customary care, outside of participation in this study);
- 9. Candidate has had previous nail matrix ablative surgery, either chemical or cold steel, on any of the involved digits;
- 10. Candidate presents systemic or local contraindications to the proposed application of the topical antifungal nail solution or the placebo agent, such as an uncontrolled cardiac, neurological, hepatic, renal, metabolic, or hematological disease or impairment that has been identified;

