- 11. Candidate suffers from malignant, or bacterial or viral infectious cause/s of nail plate dystrophy;
- 12. Candidate has a history of known immunosuppression; use of steroid agent (oral, injectable, and topical, however steroid containing inhalant for COPD/asthma is allowed) 3 months prior to baseline visit or at any follow-up;
- 13. If diabetic, the candidate has diabetes mellitus with hemoglobin A1c greater than 8% (the Hb A1c value will be determined using the last value in the participant's medical record, up to 3 months prior to enrollment, or procured in the course of the potential participant's subsequent usual and customary medical management);

CONFIDENTIAL

- 14. Candidate shows signs of substantial peripheral circulatory insufficiency defined as non-palpable pedal pulses on the involved foot or feet;
- 15. Candidate is currently participating in another surgical, device, or drug study or has participated in any research study involving an investigational device or drug, or surgical procedure, within the preceding 30 days;
- 16. Candidate is allergic to any of the study products;
- 17. Candidate is pregnant or breast feeding;
- 18. Candidate is unwilling or unable to comply with the study procedures;
- 19. Candidate is affiliated with the investigator or persons working at a study site, or patient who is an employee of the sponsor's company;
- 20. Candidate is institutionalized because of legal or regulatory order; or
- 21. Candidate is unable to provide informed consent.

Method for Assigning Participants to Treatment Groups

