to other toenails [select all that pertain]	Split, canaliformis, fragmented	5
	TOTAL SCORE (range 7 to 27)	

Table 3 Visible Nail Plate Involvement Score (VNPIS)

Study Visits and Procedures

Investigators participating in this clinical trial will undergo a thorough review of the protocol via teleconference prior to initiation of the investigation. Participating site personnel and the study sponsor, as well as the PI, have already engaged in teleconference in regard to preparation of the study materials and planned involvement. Study visits and procedures will proceed as follows:

- 1. Screening and Pre-treatment Evaluation
- 2. Initiation of Study Treatment
- 3. 3-Month Follow-up Visit
- 4. 7-Month Follow-up Visit
- 5. 9-Month Follow-up Visit

CONFIDENTIAL

When and How to Withdraw Participants

Participation in this research study is voluntary, and any participant can withdraw from the study at any time of their own choice. Although it is desired that all participants, once randomized into a treatment arm, remain in the study until completion of the follow-up visits, it may be necessary to discontinue a volunteer's participation if the participant fails to adhere to the protocol requirements, worsening of fungal infection to the involved toenail or if the participant withdraws his or her consent. Beyond the routine potential complications related to topical application of active topical nail solution, participation in this research project conveys no foreseeable safety hazards. If the volunteer desires, or if the study staff decides, to discontinue a volunteer's participation, it can be done on an immediate basis without the need for a tapered withdrawal period. Participants who choose not to continue with the study protocol until the end of the follow-up period, due to the development of a complication related to their participation in the study, or for any other reason, will be censored, and their last observed data carried forward in the statistical analyses.

Data Collection and Follow-up for Withdrawn Participants

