Secondary endpoints are changes in the participants' toenail-related quality of life, as measured using the OnyCOE-t[™] quality of life questionnaire (56,57), and changes in the appearance of the index toenail as measured using the visible nail plate involvement score. Additional demographic exposure variables will also be collected and analyzed in order to describe the participants in the study. Specifically, the participant's age, sex, body mass index (BMI), comorbidities and medications, as well as the number of mycotic toe nails, the duration of onychomycosis based on the participant's history, the presence of pedal digital deformity (hammer toe, claw toe, if present), and any local or systemic complication/s that may arise during the course of the investigation.

All participants will be followed to the endpoint of the study, in accordance with the proposed timeline. The data will be considered based on type and distribution. An intention-to-treat analysis will be used, and it will entail descriptive statistical methods, including mean and standard deviation, or median and quartile, to describe demographic variables; as well as tests of the null hypothesis that will include 2-sample Student's *t*-tests, or Wilcoxon rank sum tests, for differences between the two study groups both before and after intervention, and paired *t*-tests, or Wilcoxon signed ranks tests, for comparison of pre- and post-treatment results in single participants, for continuous data, depending on the distribution of the data. The statistician will be blind to treatment allocation, which will be denoted as "A" or "B" until the results are computed, after which time the precise nature of the allocation will be revealed.

CONFIDENTIAL

Participant Population(s) for Analysis

The specific population to be included in this intention-to-treat analysis will be the all-randomized population (any participant randomized into the study, regardless of whether they underwent topical application of active topical nail solution or the placebo). This population will be subjected to primary and secondary endpoint analyses. For any participant lost to follow, their last observation will be carried forward for the subsequent evaluations in accordance with the study timeline.

Safety and Adverse Events

Definitions

Adverse Event

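### Follow-up may stop because the nail worsens, and last observation carried forward then fills month 9: ITT is weakened, not breached, and the secondary scores bear most of the effect

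*Protocol*

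**What the plan says.** - **Ending participation.** When and How to Withdraw Participants gives three grounds: failure to adhere, "worsening of fungal infection to the involved toenail or if the participant withdraws his or her consent". What ends is participation, not only use of the solution.
- **Handling afterwards.** The same section says that participants who choose not to continue, for any reason, "will be censored, and their last observed data carried forward in the statistical analyses". The Study Summary (Statistical Methodology) is broader: "the last observation carried forward method will be used if a participant fails to complete the study protocol", for any cause of loss, random or not. Participant Population(s) for Analysis repeats LOCF for those lost to follow-up.
- **Data after withdrawal.** Data Collection and Follow-up for Withdrawn Participants asks for the reason and, with permission, at least time-to-event information. It plans no later PAS, VNPIS or OnyCOE-t.
- **The promise.** Statistical Methods states: "All participants will be followed to the endpoint of the study". The analysis population is everyone randomised, in the arm allocated.
- **Endpoints.** The primary is presence or absence of hyphae on PAS. The secondaries are OnyCOE-t and VNPIS, and VNPIS is scored at baseline and every visit. Diagnosis of Primary Outcome places the repeat PAS at the end of the intervention period, at month 3, 7 or 9.
- **Exclusions 4 and 12.** Narcotic or anti-inflammatory use is barred as "drug/s for 48 hours prior to baseline visit or at any follow-up clinical evaluations", and steroid use as "3 months prior to baseline visit or at any follow-up". Neither says what happens to a randomised participant who meets it.

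**The concern.** Worsening of the nail is itself an outcome. If it can end follow-up, data are lost because of the result being measured. LOCF then substitutes a month-0, month-3 or month-7 value for month 9. Study Duration makes month 9 the efficacy endpoint because a visible nail plate takes about 7 to 9 months to be replaced, so an earlier score is a poor proxy in either arm. Carried values are also analysed as if observed, which misstates the uncertainty.

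The instructions also conflict. Censoring belongs to a time-to-event analysis, and none is planned. Carrying a value forward does the opposite: it treats the participant as observed to the end. An analyst cannot do both. At stake are the month-9 comparisons of VNPIS and OnyCOE-t and, for a small group, the PAS result.

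**Working it through.** **1. The plan's own figure.** Inputs from Power and Sample Size Determination: cure rates 0.01 and 0.30, alpha 0.05 (two-sided assumed), 29 per arm. Beta is printed as 0.80 in the Study Summary and 0.08 in the body; I read it as 80% power. Exact Fisher power at 29 per arm is 84.3%, and the continuity-corrected formula for 80% power gives 30. Then 58 × 1.2 = 69.6, rounded to 70. The stated size reproduces and does not decide this point.

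**2. VNPIS when participants are lost while improving.** Assumptions, none from the protocol: linear change to month 9, true mean falls of 6 (active) and 2 (placebo), difference 4.0. A participant lost after month 3 keeps 3/9 of the change. With loss fractions a (active) and p (placebo):

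LOCF difference = 6 × [(1 − a) + a/3] − 2 × [(1 − p) + p/3]

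| Lost after month 3, active / placebo | Calculation | LOCF difference |
|---|---|---|
| 20% / 20% | 4 × (0.8 + 0.0667) | 3.47 (−13%) |
| 30% / 10% | 6 × 0.80 − 2 × 0.933 = 4.80 − 1.87 | 2.93 (−27%) |
| 10% / 30% | 6 × 0.933 − 2 × 0.80 = 5.60 − 1.60 | 4.00 (none) |
| 0% / 30% | 6 − 1.60 | 4.40 (+10%) |

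Timing matters too. With 20% lost in each arm, carrying baseline gives 4 × 0.8 = 3.20, and carrying month 7 gives 4 × (0.8 + 0.2 × 7/9) = 3.82.

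**3. VNPIS when worsening goes unscored.** If a share w leaves before a worsening of m points is recorded, the arm mean looks better by w × m. For assumed w of 10% to 20% and m of 2 to 4 points, that is 0.2 to 0.8 points per arm. The contrast shifts by 0 if w is equal in the arms. At 20% against 10% it shifts by 0.1 × 2 = 0.2 to 0.1 × 4 = 0.4 points, in either direction.

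**4. PAS, baseline positive.** Inclusion criterion 3 requires a positive PAS. A participant withdrawn with no later test carries that positive forward and is not cured. LOCF and failure imputation then agree. At 35 per arm, with cure rates multiplied by (1 − loss) in both arms, two-sided Fisher power is:

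| Loss in both arms | Power |
|---|---|
| 0% | 93.5% |
| 10% | 88.6% |
| 20% (rates 0.008 and 0.24) | 81.0% |
| 30% | 70.1% |

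**5. PAS, where LOCF can create a cure.** Two groups remain: participants with an early negative who are then lost, and those whom Diagnosis of Primary Outcome allows to be randomised PAS-negative (number not stated). A carried-forward absence in the second group would count as a cure without any response. With an assumed placebo cure rate of 0.01, one case can matter. At 35 per arm, 6 cures against 0 gives two-sided Fisher p = 0.025; 6 against 1 gives p = 0.106.

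**The case against.** A reader might infer more than the protocol supports.

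- **That intention to treat is not met.** Everyone randomised stays in the denominator, in the allocated arm. The weakness is incomplete follow-up with single imputation.
- **That drug use at follow-up leads to withdrawal.** No section says so. The wording sits inside exclusion criteria with no consequence stated. Removal could come only through the non-adherence ground, which is an inference.
- **That failures always keep an earlier, better score.** VNPIS is scored at each visit. If worsening is found at a visit, the worse score is the last observation and is carried forward. Only worsening after the last scored visit is hidden.
- **That a month-3 negative PAS carried to month 9 is an LOCF artefact.** The repeat PAS is due when the intervention ends, and cleared participants may stop early. A month-3 negative is normally the planned final result, so whether it suffices is a question of endpoint timing. LOCF enters only when loss follows an early negative.
- **That the censoring sentence covers everyone withdrawn.** It literally covers those who choose not to continue. Staff-ended participants are reached by the broader LOCF rule in the Study Summary.

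It is also fair to say that the protocol sets out repeated calls, certified mail and next-of-kin contact before declaring loss. It calls the PAS-negative comparison secondary, although the all-randomised definition does not keep those participants out of the primary analysis. The choice of imputation is often left to an SAP, but here the protocol itself fixes LOCF.

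These objections narrow the point. They do not remove the conflict over follow-up, the incompatible wording, or the weakness of LOCF for the repeated scores.

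**Conclusion.** The concern holds in limited form. The ground of worsening contradicts the promise to follow everyone, censoring contradicts carrying forward, and LOCF for any cause of loss is a poor basis for month-9 VNPIS and OnyCOE-t.

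Under the assumed linear falls and loss after month 3, a true difference of 4.0 would be reported as anything from 2.9 to 4.4 across the patterns shown. Hidden worsening adds a shift of up to 0.4 points either way. The falls, loss rates and worsening sizes are all assumptions, and the documents do not determine the direction of bias between arms.

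The primary PAS endpoint is mostly protected. Its exposure is limited to early negatives followed by loss and to participants randomised PAS-negative. The plan should be changed, but the point does not overturn the design or the sample size.

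**What to change.** 1. In When and How to Withdraw Participants, separate stopping the product from leaving follow-up. Keep the month 3, 7 and 9 assessments for everyone randomised unless consent is withdrawn, and score the index nail when product is stopped.
2. Delete the censoring wording and the request for time-to-event data, since no such endpoint exists.
3. For PAS, count a missing end-of-study result as not cured in both arms among baseline PAS-positive participants, with a sensitivity check such as a tipping-point analysis. Report participants randomised PAS-negative separately.
4. Replace LOCF for VNPIS and OnyCOE-t with a mixed model for repeated measures over months 3, 7 and 9. It assumes that loss depends only on observed data, which is why item 1 comes first.
5. Reconcile the follow-up wording of exclusions 4 and 12 with the withdrawal section and Statistical Methods, so that the consequence after randomisation is stated. Whatever clinical rule the sponsor adopts, keep these participants' data in the analysis.

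The cost is protocol wording and modest analysis work. The visits are already scheduled.
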